4.1.1. Planned Number of Participants and Countries

Approximately 95 adult participants are planned to be enrolled in order to achieve approximately 60 completers. Details on the definition of completers and the sample size are given in [Section 9](#).

The trial is planned to be conducted in the US in approximately 5 investigational centers.

4.1.2. Data Monitoring Committee/Safety Review Committee

An SRC comprising the Sponsor's clinical trial physician, clinical leader, PV physician, and other relevant experts will be summoned to review all safety data (including demography, vital signs, clinical laboratory tests and ECGs, AEs, concomitant medications use, local tolerability and pain, leakage assessment) available upon from the beginning of the study to completion of the first 15 days, inclusive of the sentinel cohort (cohort 1A). Following SRC decision that no safety concerns are raised based on the safety review of cohort 1A safety data up to day R15, inclusive, period 3 for cohort 1B may be initiated. Randomization to cohorts 2 and 3 will be initiated in parallel to cohort 1B.

Further details are provided in [Section 10.2](#).

4.2. Rationale for Trial Design

The trial design follows the recommendations provided in the FDA Guidance for Industry: Extended Release Oral Dosage Forms: Development, Evaluation, and Application of In Vitro/In Vivo Correlations (FDA, 1997). The objective of developing an IVIVC is to establish a predictive mathematical model describing the relationship between an in vitro property (usually the rate or extent of drug dissolution or release) and a relevant in vivo response (plasma drug concentration or amount of drug absorbed), per the FDA guidance (FDA, 1997) on the development, evaluation and application of IVIVC for extended-release oral products.

With the purpose of establishing IVIVC, the PK of 3 olanzapine extended-release sc formulations with different release rates will be characterized following a single-dose administration in participants with schizophrenia or schizoaffective disorder. The trial design will include extensive characterization of the PK profiles over 84 days after olanzapine sc administration (day R1 to day R84) to characterize fully the absorption kinetics of all 3 formulations for the purpose of IVIVC. All 3 formulations are expected to provide extended-release of olanzapine during the 84-day treatment period following single-dose sc administration and are expected to differ only in C_{max} as a consequence of a different release rate, with no burst present. The trial design also includes a single-dose administration of ZYPREXA im, before sc administration of one of the 3 sc olanzapine extended-release formulations. The obtained PK data of this im immediate-release formulation will be used to characterize olanzapine disposition for the purpose of IVIVC analysis. These analyses will be conducted and reported separately from the main trial results.

4.3. Access to Trial Intervention After End of Trial

Upon the completion of Follow-up Period on day R84, investigators should advise participants to return to the care of their primary physician for continuation of treatment with available medications.

4.4. Start of Trial and End of Trial

The trial start date is the date on which the clinical trial will be open for recruitment of participants. The first act of recruitment is the first investigational center open and will be the trial start date. EOT is defined as the last follow-up visit of the last participant.

5. TRIAL POPULATION

5.1. Selection of Trial Population

The trial population will include participants 18 to 64 years of age, with a diagnosis of schizophrenia or schizoaffective disorder. Participants must be clinically stable, not currently on antipsychotic treatment, with the exception of oral treatment with aripiprazole, risperidone, paliperidone, quetiapine, or lurasidone, and meet all trial eligibility criteria. During period 3, participants will be treated with 1 of 3 single-dose sc olanzapine extended-release formulations. For details regarding the study design, refer to Section 4.1.

5.2. Rationale for Trial Population

The selected trial population is representative of the demographics and disease state of individuals who are likely to be treated with TV-44749 in a clinical setting.

5.3. Inclusion Criteria

Participants may be included in this trial only if they meet all of the following criteria:

- a. Capable of giving signed informed consent as follows:
 - Able to understand the nature of the trial and any possible hazards in participating; willing to provide written informed consent to participate; and after reading the trial information and consent form and having the opportunity to discuss the trial with the Investigator or assigned delegate, sign the informed consent form (ICF).
 - Able to follow protocol requirements, including the prescribed dosage regimens, tablet ingestion, sc depot injection, and discontinuation of prohibited concomitant medications; able to participate in and comply with the requirements of the entire trial; able to read and understand the written word in order to complete participant-reported outcomes measures; and can be reliably rated on assessment scales.
- b. Males or females of any ethnic origin aged 18 to 64 years, inclusive, at the time of screening.
- c. Body weight >50 kg and body mass index (BMI) within the range 18.5 to 38.0 kg/m², inclusive, at the time of screening.
- d. Agree to maintain current smoking or nonsmoking status at the time informed consent is obtained and throughout the trial until completion of the end of treatment or early termination (ET) visit (ie, nonsmoking participants must agree not to start smoking and participants who smoke will be excluded if they plan to discontinue smoking during the trial).
- e. Agree to the inpatient periods required during the trial period.
- f. Have a current confirmed diagnosis of schizophrenia or schizoaffective disorder according to an evaluation by the Investigator, using the Diagnostic and Statistical

Manual of Mental Disorders, Fifth Edition (DSM-5) ([American Psychiatric Association 2013a](#)).

- g. Are clinically stable, on oral aripiprazole, risperidone, paliperidone, quetiapine, or lurasidone (ie, dose has not changed in the last 4 weeks prior to screening) and not currently on other antipsychotic including olanzapine treatment at the time of screening.
- h. Have a [REDACTED] score ≤ 70 and a [REDACTED] score ≤ 3 at the time of screening.
- i. Have had no hospitalization for worsening of schizophrenic symptoms and no significant exacerbation of schizophrenic symptoms, as judged by the Investigator, within the 3 months prior to screening.
- j. Have no ongoing or expected significant life events (eg, pending loss of housing, marital status change, long travel abroad, surgery) that could affect trial outcomes throughout the period of trial participation.
- k. [Revision 1] Women may be included only if they have a negative serum beta human chorionic gonadotropin (HCG) test result at screening; they are surgically sterile (hysterectomy, bilateral salpingectomy, or bilateral oophorectomy) or postmenopausal (postmenopausal status will be confirmed by a follicle-stimulating hormone screen according to the clinical laboratory standard value) for at least 1 year; or they are practicing a highly effective method of birth control and not planning pregnancy for at least 30 days before the trial, for the duration of the trial, and for 70 days after the last dose administration, if they are sexually active and of childbearing potential (Section 13.1).
- l. Men must be sterile; or if they are potentially of reproductive competence and have sexual relationship with female partners of childbearing potential, they must use, together with their female partners, highly effective birth control methods for the duration of the trial and for 70 days after the last dose administration.
- m. Willing and able to comply with trial restrictions and to remain at the investigational center for the required durations during the trial period and willing to return to the investigational center for the follow-up procedures and assessments as specified.

5.4. Exclusion Criteria

Participants will be excluded from participating in this trial if they meet any of the following criteria:

- a. Presence or have a history of clinically significant diseases of the renal, hepatic, gastrointestinal, cardiovascular, or musculoskeletal system, or presence or history of clinically significant immunological, endocrine, or metabolic diseases, neurological or psychiatric disorder(s) (other than schizophrenia), or a history of any illness that, in the opinion of the Principal Investigator, might pose additional risk to the participant by participation in the trial or confound the results of the trial.

b. Infectious disease:

- Acute infection and/or antibiotic treatment must be resolved 28 days prior to the first dose of IMP.
- Any chronic infection.
- [Revision 1] Known history of, or a positive test result for hepatitis B surface antigen and/or core antibody, known history of, or positive serology for hepatitis C and positive ribonucleic acid (RNA) test*, human immunodeficiency virus Types 1 or 2 antibody (according to enzyme-linked immunosorbent assay test), or active/latent tuberculosis (as determined by a positive result of the QuantiFERON test). If the QuantiFERON test result is indeterminate, then the test may be repeated once. If the second QuantiFERON test result is indeterminate also, the participant will be excluded from the study.

*Note: If serology is positive but the RNA test is negative, and the patient has no history of liver disease or symptoms of active liver disease, enrollment will be allowed based on clinical judgment.

- c. History or known risk of narrow-angle glaucoma.
- d. Uncontrolled diabetes (hemoglobin A1c 6.5% or above and/or fasting plasma glucose 126 mg/dL or above).
- e. Major trauma or surgery in the 2 months before screening or at any time between screening and the first dose of IMP, or surgery scheduled during the trial or follow-up period, or open biopsy within 4 months prior to screening.
- f. History of malignancy or treatment of malignancy in the last 5 years, excluding resected basal cell or squamous cell carcinoma of the skin.
- g. The participant is a pregnant or lactating woman or plans to become pregnant during the trial or within 70 days after the last dose administration.
- h. The patient has current or a history of known hypersensitivity to olanzapine or any of the excipients of TV-44749 or the oral formulation of olanzapine, or ZYPREXA im in any formulation.
- i. Presence of excessive pigment, bruises, scars, or tattoos around the potential injection area.
- j. Presence of any local skin infection, rash, or anything else that limits injection administration and assessment of injection site.
- k. Donated or received any blood or blood products (eg, white blood cells, platelets) within 60 days prior to screening, or has donated blood or blood products on 2 or more occasions within 6 months prior to IMP administration, or has donated plasma within 7 days prior to screening, or has planned donations during the 56 days or 5 half-lives following the last dose administration, whichever is longer. The minimum reference volume of whole blood lost or donated is 500 mL.
- l. Vulnerable participants (eg, prisoners or institutionalized individuals), participants who pose a significant risk of suicide attempt in the Investigator's judgment based on

medical history, answered “yes” to Suicidal Ideation items 4 or 5 on the [REDACTED] for “current” or “within 3 months prior to screening,” or had a suicide attempt or hospitalization due to suicide risk within 12 months prior to screening.

- m. 12-lead electrocardiogram (ECG) demonstrating intraventricular conduction delays (QRS interval \geq 110 msec or PR interval \geq 200 msec) and have a mean of triplicate QTcF values $>$ 450 msec for males and $>$ 470 msec for females at screening or other clinically significant ECG findings that would interfere with trial participation as judged by the Investigator.
- n. Personal or family history of arrhythmia, sudden unexplained death at a young age (before 40 years) in a first-degree relative, long QT syndrome, personal history of syncope, or history of uncontrolled high blood pressure. Participants with history of high blood pressure who no longer require treatment or participants who are treated with antihypertensive medications and whose blood pressure is currently well-controlled, may be enrolled.
- o. Supine or semi-supine blood pressure outside the range of 90 to 140 mm Hg for systolic or 50 to 90 mm Hg for diastolic (following at least a 5-minute rest). Note: If either value is out of range, blood pressure measurements may be repeated in the supine or semi-supine position at intervals of 5 to 10 minutes up to 2 times. If the systolic or diastolic measurement continues to exceed the stated limits, the participant will be excluded.
- p. Orthostatic hypotension defined as a decrease exceeding 20 mmHg in systolic blood pressure or 10 mm Hg in diastolic blood pressure, or both, occurring within 3 minutes of changing from supine to standing position, or orthostatic intolerance (only 2 rechecks of orthostatic blood pressure are permitted for eligibility purposes).
- q. Postural tachycardia defined as a sustained heart rate increment of 30 beats per minute within 10 minutes of standing (only 2 rechecks allowed).
- r. [Revision 1] Body temperature (measurement performed either orally or on both ears, recording the highest value) outside the interval of 35.4°C to 37.5°C at the screening visit.
- s. [Revision 1] Clinical laboratory test abnormalities as listed below:
 - Clinical laboratory values with Common Terminology Criteria for AEs (CTCAE) Grade 2 or above
 - Blood urea nitrogen $>$ 31 mg/dL
 - Lactate dehydrogenase \geq 3 \times upper limit of normal (ULN)
 - Urinalysis with any clinically significant finding
 - Total bilirubin $>$ 2.5 mg/dL
 - Alanine aminotransferase (ALT) or aspartate aminotransferase (AST) $>$ 2 \times ULN
 - Creatinine $>$ 2 \times ULN

- Creatine phosphokinase (CPK) $>3 \times$ ULN. Participants with CPK levels $>1.5 \times$ ULN and $\leq 3 \times$ ULN may be enrolled, if the results are not clinically significant according to the Investigator's review and judgment, in consultation with the Sponsor's medical representative.
- International normalized ratio ≥ 2.0
- Absolute neutrophil count $<1.5 \times 10^9/L$

Any laboratory abnormality may be retested once per the Investigator's clinical discretion. If the retested value is within normal limits, the participant does not need to be excluded from the trial. The retest limitation applies to the same day laboratory assessments but not to monitoring for trends (eg, CPK). Abnormal laboratory values that meet CTCAE Grades 1 and 2 may be accepted per consultation with Sponsor and where safety is not compromised. The severity of each clinical laboratory AE will be graded according to CTCAE, version 5.0.

- t. Any procedure or disorder that may interfere with drug absorption, distribution, metabolism, or excretion (appendectomies are acceptable procedures at the discretion of the Investigator).
- u. Received a prolonged-release formulation of olanzapine within 5 half-lives prior to screening.
- v. Use of an investigational drug or marketed drug (new chemical entity) within 30 days or 5 half-lives (whichever is longer) or in case of biologics (eg, tumor necrosis factor-alpha inhibitors such as adalimumab, etanercept, or infliximab) within 3 months or 5 half-lives (whichever is longer) prior to the administration of ZYPREXA im.
- w. Using or consuming the following concurrent medications, over-the-counter (OTC) products, prescription drugs (any route of administration: eg, oral, topical), or foods:
 - strong and moderate inducers or inhibitors of CYP1A2 (Section 13.4) within 30 days or 5 half-lives (whichever is longer) prior to the administration of ZYPREXA im.
 - dopamine reuptake inhibitors or prescription psychostimulants within 30 days prior to screening.
 - opioids or opioid-containing analgesics within 30 days prior to screening.
 - medications, in addition to those listed above, that may be expected to significantly interfere with the metabolism or excretion of olanzapine, that may be associated with a significant drug interaction with olanzapine, or that may pose a significant risk to participants if they were enrolled in the trial.
- x. Meets criteria for moderate to severe substance use disorder (based on DSM-5 criteria) within the past 6 months, such as chronic alcohol abuse or drug abuse (excluding those related to caffeine or nicotine). If, per the Investigator's judgment, a participant does not meet the criteria for substance use disorder, a positive result on the serum drug test is not exclusionary. Participant's eligibility in cases of a positive

result, without medical explanation, will be determined by the Investigator based on the participant's background, history of substance use, and the Investigator's discussions with family members, caregivers, or healthcare professionals, as applicable ([American Psychiatric Association 2013b](#)).

- y. Treatment-resistant schizophrenia according to medical and psychiatric history as judged by the Investigator or have taken clozapine for treatment-resistant schizophrenia.
- z. A significant sedation or delirium post-antipsychotic treatment according to medical and psychiatric history and as judged by the Investigator or suffered from delirium due to a medical condition.
 - aa. A significant risk of violent behavior based on the participant's medical and psychiatric history as judged by the Investigator.
 - bb. [Revision 1] A current clinically significant DSM-5 diagnosis other than schizophrenia or schizoaffective disorder.
 - cc. History of or a current active medical condition that may either compromise the participant's safety or interfere with the safety or outcome evaluation of the trial drug, including, but not limited to, traumatic brain injury or seizure (excluding a single febrile or withdrawal seizure), neuroleptic malignant syndrome, clinically significant tardive dyskinesia, or are suffering with a clinically significant neurological disorder.
- dd. The participant cannot participate or successfully complete the trial, in the opinion of the Investigator, for any of the following reasons:
 - The participant is under the legal age of consent, mentally or legally incapacitated, or unable to give consent for any reason (unless a legal guardian is able to provide consent according to local requirements).
 - The participant is in custody due to an administrative or a legal decision, or under tutelage, or being admitted to a sanitarium or social institution.
 - The participant is unable to be contacted in case of emergency or in case a follow-up assessment is required within 30 days after trial completion.
 - The participant is an employee of the Sponsor or the site or a relative of an employee at the site conducting the trial.
 - Any other reason, at the discretion of the Investigator.

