3.2. Primary Estimand

For the primary objectives, the estimand is described by the following attributes:

- a. Population – adult participants, 18 to 64 years of age, with a clinically stable diagnosis of schizophrenia or schizoaffective disorder, not currently on antipsychotic

treatment, with the exception of oral treatment with aripiprazole, risperidone, paliperidone, quetiapine, or lurasidone, and meeting all trial eligibility criteria. For intercurrent events which could adversely affect the calculation of the PK parameters, the participant will be excluded.

- b. Endpoint – see parameters in Section 3.1.
- c. Treatment – the 3 formulations of Olanzapine for Extended-release Injectable Suspension, with different release rates, over the 84-day olanzapine sc treatment period (day R1 to day R84) following single-dose administration.
- d. Population level summary – descriptive statistics (n, mean, standard deviation, geometric mean [if appropriate], geometric coefficient of variation (%CV) [if appropriate], median, minimum, and maximum).

Rationale for estimand: To characterize the PK of 3 olanzapine extended-release sc formulations with different release rates, following single administration in participants with schizophrenia or schizoaffective disorder, who are clinically stable and are not on antipsychotic treatment, with the exception of oral treatment with aripiprazole, risperidone, paliperidone, quetiapine, or lurasidone, and who meet all trial eligibility criteria.

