5.5. Ongoing Confirmation of Participant Eligibility

Participants' continued eligibility will be reconfirmed by review of abbreviated inclusion and exclusion criteria prior to administration of ZYPREXA im. The abbreviated list will include the following inclusion criteria (g, h) and exclusion criterion (a). Clinical scales and laboratory tests taken on day 1 will be used to confirm eligibility on day 3. In case of a delay, laboratory results can be reviewed to perform abbreviated eligibility assessment on day 4, as long as this is done prior to administration of ZYPREXA im. Laboratory results from blood samples collected on day 4 are not required prior to initiating ZYPREXA im. Day 4 central clinical laboratory

assessments will serve as baseline values and are based on samples collected prior to dosing of ZYPREXA im. Serology to support eligibility criteria will only be done at screening.

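### Exclusion criterion a exempts only schizophrenia, so on its plain reading it excludes schizoaffective disorder, one of the trial's two target diagnoses

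*Protocol*

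**What the plan says.** Section 5.4 of the protocol opens with a rule that makes each criterion sufficient on its own: "Participants will be excluded from participating in this trial if they meet any of the following criteria". Criterion a then lists organ-system diseases and continues with "neurological or psychiatric disorder(s) (other than schizophrenia), or a history of any illness that, in the opinion of the Principal Investigator", ending with a clause about added risk to the participant or confounding of the results.

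Other parts of the protocol define the population with two diagnoses:

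- Inclusion criterion f (Section 5.3): "Have a current confirmed diagnosis of schizophrenia or schizoaffective disorder according to an evaluation by the Investigator".
- Primary estimand (Section 3.2): adults "with a clinically stable diagnosis of schizophrenia or schizoaffective disorder". SAP Section 1.2 also names both diagnoses. Both estimands further require that all eligibility criteria be met.
- Exclusion criterion bb (Section 5.4): "A current clinically significant DSM-5 diagnosis other than schizophrenia or schizoaffective disorder".
- The title and Section 5.1 also name both diagnoses.

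Section 5.5 sets out the eligibility re-check before ZYPREXA im. It names criterion a as the only exclusion criterion on the abbreviated list, alongside inclusion criteria g and h. Section 6.6.1 forbids enrolment through waivers or exemptions.

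**The concern.** Schizoaffective disorder is a psychiatric disorder, and criterion a does not exempt it. A person can therefore qualify under f, pass bb, and still meet a.

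Two outcomes are possible. A centre that applies a as written turns away a diagnosis the trial means to enrol. A centre that follows f and bb enrols people who meet a written exclusion, with no waiver route to cover them. With approximately 5 centres, screening could differ from one to the next. Section 11.2 requires a centre that learns someone was entered without meeting the criteria to tell the sponsor at once, and it calls such an entry an important protocol deviation. SAP Section 5.8 summarises important deviations, so the conflict could reach the study report.

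**Working it through.** No arithmetic applies. The plan states no figure on this point, and Protocol Section 9.8 says no formal sample size calculation was done. The check sets the passages side by side and follows one case through them: a candidate who satisfies f through schizoaffective disorder.

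1. **Is the disorder within the scope of a?** Yes. Criterion a covers psychiatric disorders, present or past.

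2. **Does the exemption reach it?** Not on the wording. The exemption names schizophrenia only. Criteria f and bb list schizophrenia and schizoaffective disorder as separate alternatives, so within these same lists the first term does not include the second.

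3. **Does the clinical-significance qualifier let the candidate through?** It is hard to argue so. Criterion f requires a current DSM-5 diagnosis, and criterion g requires that participants "Are clinically stable, on oral aripiprazole, risperidone, paliperidone, quetiapine, or lurasidone". A confirmed diagnosis on maintenance antipsychotic treatment is not easily called insignificant, and a also covers history. Criterion bb carries the same qualifier, and the sponsor still found it necessary to add schizoaffective disorder there.

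4. **What follows from meeting a?** Exclusion. Section 5.4 makes any one criterion sufficient, and Section 6.6.1 closes the waiver route.

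5. **Was the difference between a and bb intended?** Nothing in the documents says so. Administrative Letter 01 (26 March 2024) corrected bb in order to align it with the population in f and in the title, and Amendment 01 (11 May 2024) incorporated that correction. In the current text bb carries a revision tag. Criterion a carries none, and the list of changes has no entry for it. The stated reason for correcting bb applies equally to a.

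6. **Does the conflict come up again?** Yes, formally. Section 5.5 and Table 1, footnote d, place criterion a on the list to be reconfirmed before ZYPREXA im.

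**The case against.** The strongest reply is that the last clause of a, on the Principal Investigator's opinion about risk or confounding, may govern the whole list. Exclusion would then be a judgment, and a target diagnosis would hardly be judged a risk or a confounder. The sentence can be read that way, but the clause attaches most naturally to the illness history immediately before it. Even on the wider reading, it would leave a target diagnosis to each investigator's discretion without exempting it.

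The second reply is that the intent is plain and that the protocol sometimes uses schizophrenia as shorthand. Section 6.2.1 describes an earlier trial's dose range as tested in participants with schizophrenia, although Section 2.1.3 says that trial also took schizoaffective participants. Most centres may well follow f and bb, and the documents contain no sign that any centre has screened people out under a. This limits the likely harm. It does not remove the contradiction, because participants so enrolled would still meet a written exclusion.

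Four stronger readings are tempting, and the documents do not support them:

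- **A headcount.** A reader might multiply an assumed schizoaffective share by the approximately 95 planned participants. The documents give no share, and people screened out under a never join the 95. Enrolment is also competitive (Section 13.6), so a slot one centre cannot fill passes to another.
- **Bias in the results.** The analysis is descriptive pharmacokinetics with no inference. Cohorts 1B, 2 and 3 are randomized 4:5:5, so a diagnosis mix that varies by centre does not by itself bias comparisons among them. Nothing in the documents says olanzapine pharmacokinetics differ between the two diagnoses.
- **Every such enrolment is certainly an important deviation.** The definition in Section 11.2 says such deviations may include nonadherence to entry criteria, and it ties importance to a significant effect on participants or on scientific value. A later paragraph of the same section does label ineligible entry important. The classification is therefore arguable.
- **A fresh diagnostic review on day 3 or 4.** The re-check relies on day 1 scales and laboratory tests and is not described as a new diagnosis. It does still cite criterion a.

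**Conclusion.** The point holds as an internal contradiction in an operative eligibility rule. On its plain reading, criterion a excludes schizoaffective disorder, while the title, f, Section 5.1, the primary estimand and bb include it. The estimand is affected only in this sense: it names a diagnosis that its own requirement to meet all eligibility criteria would remove. A centre applying a literally would still enrol people inside the definition, but from a narrower group.

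The consequence is a risk of uneven screening between centres, or of schizoaffective participants who technically meet an exclusion. Its size in participants cannot be stated from the documents, and no effect on the pharmacokinetic summaries is shown. The conclusion rests on reading schizophrenia in a as it is used in f and bb, and on attaching the investigator-opinion clause to the illness history. It should be corrected, but it does not threaten the trial's primary objective.

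**What to change.** Reconcile criterion a with f and bb by making its parenthetical exemption read: other than schizophrenia or schizoaffective disorder. This is the exemption bb already uses, so it brings in no new eligibility rule. Sections 5.5 and Table 1 need no edit, because they cite criterion a by letter and take the correction automatically.

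The cost is a few words in the next amendment, or in an administrative letter, the route already used for bb. The amendment reports 6 participants enrolled, all in cohort 1A, as of 3 May 2024, against approximately 95 planned. At that date, most enrolment (about 95 − 6 = 89) could still have been screened under the corrected text.
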